5.2 Interim Analysis

Interim statistical analyses of clinical trials will be at least once a year to review trial results; however, the exact timing of the interim analyses is at the discretion of the PI. A formal detailed statistical report will be written by the PI which presents the results of every aspect of the study, including all baseline variables, protocol adherence, all outcome variables, adverse events reported and center performance in terms of recruitment, data quality, loss to follow-up and protocol violations. However, the main emphasis is on the primary outcome as well as maternal safety outcomes. It is recognized that any decision to terminate the study would not be reached solely on statistical grounds but on a number of complex clinical and statistical considerations.

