3.5.3 Randomization and Masking

After obtaining informed consent, women undergoing an induction of labor for preeclampsia will be randomized to either 30mg IMN given intravaginal with placement of misoprostol/foley bulb (as clinically indicated) or placebo in a 1:1 ratio. Randomization in each group will be by simple randomization, and will be computer generated. A confidential computer-generated simple randomization will be prepared and provided on an ongoing basis to a designated investigational pharmacist (all other study staff will be blinded). The investigational pharmacy will prepare identical appearing suppositories of IMN (30mg) or placebo according to the randomization sequence and deliver to a dedicated secure area in the labor and delivery area. A randomization log with study medication number, patient name and medical record number will be used to track the randomization process.

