- neonatal blood transfusion

- hypoxic–ischemic encephalopathy
- intraventricular hemorrhage grade 3 or 4
- necrotizing enterocolitis
- receipt of head cooling
- Other neonatal outcomes analyzed will be neonatal intensive care unit admission, neonatal intensive care unit admission greater than 48 hours, and neonatal length of stay (days).

5. Statistical Considerations

5.1 Sample size calculation:

Using data from our prior studies using the intended study population at The Ohio State Wexner Medical Center the incidence of gestational hypertension or preeclampsia is 10-15%.

Data abstracted from those enrolled in biorepository for gestational hypertension or preeclampsia over one year period and excluding those who were delivered for gestational hypertension or preeclampsia who had cesarean section for breech, prior cesarean section or uterine surgery, HELLP syndrome, eclampsia.

295 women underwent induction of labor for gestational hypertension or preeclampsia 48% (n=141) ended up with cesarean delivery after failed induction of labor or non-reassuring fetal well being.

Gestational Age Distribution for Gestational Hypertension or Preeclampsia Induction

Gestational Age in weeks	Number of women IOL for gHTN or PE	CS rate
24-28 wks	13	10 (77%)
28-30 wks	15	11 (73%)
30-32 wks	26	18 (69%)
32-34 wks	39	19 (49%)
34-36 wks	56	20 (34%)
36-37 wks	35	12 (34%)
37-38 wks	57	22 (38%)
38-39 wks	17	3 (18%)
39-40 wks	8	2 (25%)
40-41 wks	2	1 (50%)

Review of literature reveals is similar to OSU numbers, with the overall rate of cesarean delivery after induction of labor for gestational hypertension or preeclampsia ranges from 40% to 70%. Based on available data, we anticipate that the expected rate of the primary outcome in the women undergoing induction of labor for gestational hypertension or preeclampsia 45%. For this proposal, we will estimate a conservative relative reduction effect of 30-35%.

The table below provides the sample size calculations needed to achieve 80-90% power to detect 30-35% difference in the primary outcome between women receiving IMN or placebo at time of their induction of labor for preeclampsia, using a two-tailed alpha of 0.05.

Table 1. Total sample size required to detect a difference in primary outcome in women undergoing induction of labor and receiving IMN or placebo (alpha at 0.05, variable primary outcome rates, power, and effect sizes)

Relative reduction (%)	Power (%)	Primary Outcome Rate in Placebo group				

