		35%	40%	45%	50%	55%
30	90	784	644	540	462	380
	85	670	550	460	394	326
	80	586	480	404	346	284
33	90	656	540	430	368	306
	85	562	462	368	316	276
	80	490	404	322	276	242
35	90	586	482	406	330	290
	85	502	412	348	282	248
	80	438	362	304	248	216

Assuming the primary outcome to be 45 %, close to 1:1 enrollment and anticipating that no more than 2% of randomized women to be lost to follow up, a sample size of 400 women will achieve >85% power to detect a 33% relative reduction in primary outcome overall.

Given the study design and that randomization will occur once decision to proceed with induction occurs, there will be no concern for loss to follow up or missing outcome data on any women. Regarding concern for non-compliance, given study design we propose that it is unlikely that participant would not get their assigned treatment.

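### Section 5.2 requires uncapped, investigator-timed interim looks at the primary outcome but sets no efficacy limit, adjusted final level or bar on stopping for benefit, so the two-sided 0.05 is unprotected if a favourable by-arm look can end the trial

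*Combined protocol and SAP*

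**What the plan says.** Section 5.2 makes interim analysis mandatory and sets only a minimum frequency: "Interim statistical analyses of clinical trials will be at least once a year to review trial results". Timing is left open: "however, the exact timing of the interim analyses is at the discretion of the PI". On content, "A formal detailed statistical report will be written by the PI which presents the results of every aspect of the study", and "the main emphasis is on the primary outcome as well as maternal safety outcomes". On stopping, "any decision to terminate the study would not be reached solely on statistical grounds but on a number of complex clinical and statistical considerations".

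Section 5.1 sizes the trial "using a two-tailed alpha of 0.05" and concludes that "a sample size of 400 women will achieve >85% power to detect a 33% relative reduction". Section 5.5 specifies intention-to-treat but gives no significance level for the final test and does not mention the interim looks.

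Neither 5.2 nor any other section gives a maximum number of looks, an efficacy limit, an alpha-spending function, an adjusted final level or a statement that the trial cannot be stopped for benefit.

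**The concern.** Testing accumulating data repeatedly at the same nominal level gives chance several opportunities to produce a significant result. Section 5.2 combines the features that make this matter: the primary outcome is reviewed, reviews recur without a cap, the investigator chooses when, and the review can contribute to ending the trial. The usual protections are absent.

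At stake is the error rate of the trial's one primary claim, that the study drug lowers the cesarean rate. If the trial stopped early on a favourable comparison, or reached its end after several such comparisons, a p-value below 0.05 could not be taken at face value. The gap also cannot be closed convincingly once by-arm results have been seen.

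**Working it through.** **Inputs.** From 5.1: placebo rate 45%, relative reduction 33%, two-sided 0.05, N = 400, at most 2% lost. From 3.5.3: 1:1 allocation. From 5.4: 132 women randomized per year.

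**The plan's own power figure.** With p1 = 0.45, p2 = 0.45 × 0.67 = 0.3015, mean rate 0.37575 and n women per arm, the two-proportion test without continuity correction gives

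power = Φ{[(p1 − p2)√n − 1.96 √(2 × 0.37575 × 0.62425)] / √(0.45 × 0.55 + 0.3015 × 0.6985)}.

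- n = 200: (2.1001 − 1.3424)/0.6768 = 1.119, power 86.9%.
- n = 196 (400 × 0.98 = 392 women): (2.0790 − 1.3424)/0.6768 = 1.088, power 86.2%.

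The stated figure of more than 85% reproduces for a single test at 0.05.

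**Look times.** 400/132 = 3.03 years. The yearly minimum gives looks at 132 and 264 women. A year-3 look would fall at 396, in effect the final analysis, and is not counted separately.

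**Assumptions not in the plan.** Each look compares cesarean rates by arm at an unadjusted two-sided 0.05, and a crossing ends the trial.

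**Type I error.** With no true difference, the test statistics at 132, 264 and 400 women are jointly normal with mean 0, variance 1 and correlations √(132/264) = 0.707, √(132/400) = 0.574 and √(264/400) = 0.812. Numerical integration gives the chance of first exceeding 1.96 in one direction as 2.50% at the first look, 1.66% at the second and 1.22% at the third, a sum of 5.38%.

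- Crossings in either direction stop the trial: 2 × 5.38% = 10.75% (before rounding). A simulation of 400,000 binary trials at 45% in both arms gave 10.8%.
- Only favourable looks stop the trial, with a two-sided final test: 5.38% + 2.50% = 7.9%.
- False claims of benefit alone: 5.4%, against 2.5% with one final test.

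**With a limit in place.** Haybittle-Peto at 132 and 264 (p<0.001, |Z| > 3.291) and a final test at 0.0495 give an overall two-sided error of 5.0%. Power by the same uncorrected test is 86.8% at N = 400 and 86.1% at 392.

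**The case against.** The strongest reply is that the inflation is conditional. Section 5.2 names no interim test or threshold, does not say that results are shown by arm, and says that stopping would not be decided on statistics alone. If the looks are pooled, or for safety only, or cannot stop the trial for benefit, the final 0.05 stands. This is correct and limits the claim. It does not remove the omission: the plan never says that the looks are of that harmless kind, and a decision that is partly statistical is not a limit. Discretion may lower the error, but by an amount nobody can state.

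Four stronger readings are tempting and are not supported.

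- **That the trial's error rate is 10.75%.** That figure counts crossings in both directions. The hypothesis is directional, and for a trial stopped only on favourable looks the figures are 7.9% in total and 5.4% for false benefit.
- **That the error is 15% to 20%.** Six-monthly looks would give about 15.7% and quarterly looks about 20.9%, again counting both directions. Section 5.2 permits such schedules but does not plan them.
- **That accrual of 5 to 6 women per week (section 6.1) should set the look times.** That figure explains pharmacy stock. It implies 5 × 52 = 260 to 6 × 52 = 312 women per year, against about 264 eligible in 5.4, so the upper end exceeds everyone eligible and the lower end needs 260/264 = 98% consent.
- **That the report by the principal investigator breaks the blind.** Section 3.5.3 says of everyone but the pharmacist that "all other study staff will be blinded", but 5.2 does not say whether the report is by arm. That is unstated, not a contradiction.

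**Conclusion.** The omission is certain from the text: mandatory, uncapped, investigator-timed looks with emphasis on the primary outcome, and nothing that protects the two-sided 0.05. The inflation is conditional on by-arm looks tested at 0.05 and on a significant look ending the trial. Under those assumptions and the accrual in 5.4, the two-sided error is about 10.75% with stopping in either direction. With stopping only for benefit it is about 7.9%, and the chance of a false claim of benefit roughly doubles (5.4%/2.5% = 2.2). More looks would raise these figures; pooled or safety-only looks would leave the error at 5%. The point should be settled before any by-arm comparison is made, because it concerns the primary claim and the remedy is cheap.

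**What to change.** Write one of two options into 5.2.

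- **Option A.** Cap the interims at one or two, set by number of women with outcomes, for example at 132 and 264. Use Haybittle-Peto p<0.001 at each interim and 0.0495 at the final analysis of 400. Repeat the final level in 5.5. If one of these two interims is dropped, 0.0495 remains safe, since removing a look can only lower the error.
- **Option B.** State that the trial will not stop for efficacy and that the final test is at 0.05.

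**Cost.** Both options are wording changes and need no extra patients. Option A moves power from 86.9% to 86.8% at N = 400 and from 86.2% to 86.1% at 392, so the stated figure of more than 85% holds. That rests on the uncorrected two-proportion test. Section 5.5 names no test for the primary outcome, and with a continuity correction the single-test power is already 84.5% and 83.7%, so the test should be named too. Option A also presupposes a by-arm comparison; who runs it under 3.5.3 is a separate masking matter for the sponsor to state. Option B loses no power, but a large early benefit would not end the trial.

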5.3 Unblinding Criteria

This is a double-blind study—neither the patients nor the physician/health care providers are aware of the drug allocation during the duration of the study. In the event of a SAE thought to be related to the study drug, the patient will be treated as if she has received IMN. If medical care requires unblinding of the medication, the pharmacist will unblind the patient treatment assignment and notify the PI.

5.4 Feasibility: There are 5000 deliveries per year in at The Ohio State Wexner Medical Center and approximately 8% of women are diagnosed with gestational hypertension or preeclampsia and approximately 2/3 undergo induction of labor therefore approximately 264 women per year would be eligible for enrollment. Given the high-risk nature of this population it is reasonable to anticipate a consent and randomization rate which is higher than that which is accounted for above. With only 50% consent rate, 132 women may be randomized annually. Our conservative estimate suggests that this study can be completed in approximately 3 years.

5.5 Data analysis: Analysis will be by intent-to-treat. Preliminary analyses will be conducted to test homogeneity of treatment groups for demographic data (gravidity, gestational age at randomization, race/ethnicity, BMI, number of prior cesarean) using the two-sample *t* test for continuous measurements and the Pearson chi-square test for categorical measurements. Primary and secondary outcomes will be analyzed between the two groups using univariable and multivariable analyses as needed.

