3.4 Eligibility Criteria

3.4.1 Inclusion Criteria:

- Women older than 18 years at the time of induction of labor with the ability to give informed consent
- Induction of labor for clinical diagnosis of preeclampsia
- Unfavorable cervix (Bishop's score of less than 6) See below
- Cervical dilation 2cm or less
- Singleton
- Gestational age \geq 24 weeks
- English speaking

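### Section 5.5 does not fix which analysis decides cesarean delivery; prespecifying adjustment for gestational age would do so and, if the trial resembles the sponsor's cohort, add about 2 points of power at no cost in women

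*Combined protocol and SAP*

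**What the plan says.** Section 5.5 (Data analysis) sets intention-to-treat and then describes baseline testing: "Preliminary analyses will be conducted to test homogeneity of treatment groups for demographic data (gravidity, gestational age at randomization, race/ethnicity, BMI, number of prior cesarean", by t test or Pearson chi-square. The next sentence is all that is said about outcomes: "Primary and secondary outcomes will be analyzed between the two groups using univariable and multivariable analyses as needed". No other section names the test or model for cesarean delivery.

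Section 5.1 gives the design values. The sample size is calculated "using a two-tailed alpha of 0.05", the effect is relative ("we will estimate a conservative relative reduction effect of 30-35" percent), and the conclusion is that "a sample size of 400 women will achieve >85% power to detect a 33% relative reduction in primary outcome overall". That is an unadjusted two-group calculation with a 45% placebo rate and up to 2% loss.

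Section 5.1 also reports the sponsor's cohort: "295 women underwent induction of labor for gestational hypertension or preeclampsia 48% (n=141) ended up with cesarean delivery". A table titled "Gestational Age Distribution for Gestational Hypertension or Preeclampsia Induction" breaks the cesarean rate down by week. Section 3.5.3 specifies simple 1:1 randomization, so gestational age is not balanced by design.

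**The concern.** The primary result could come from an unadjusted comparison or from a model with covariates chosen later, and the plan does not say which one counts. Because the sentence follows directly on the baseline homogeneity tests, one natural reading is that adjustment happens only if an imbalance shows up. The text does not state that rule. It could equally mean an unadjusted primary test with supportive models.

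Two things are at stake. One is a data-dependent choice between analyses that can fall on opposite sides of 0.05. The other is efficiency: a strong prognostic variable is recorded for every woman but is committed only to a baseline comparison.

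**Working it through.** **1. The plan's own figure.** Inputs from 5.1: p0 = 0.45; 33% relative reduction, so p1 = 0.45 × 0.67 = 0.3015; 400 women less 2% = 392, so n = 196 per arm; two-sided 0.05. With p̄ = (p0 + p1)/2 = 0.37575:

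power = Φ{[(p0 − p1) − 1.96·√(2p̄(1 − p̄)/n)] / √[p0(1 − p0)/n + p1(1 − p1)/n]}

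= Φ{[0.1485 − 1.96 × 0.0489] / 0.0483} = Φ(1.09) = 86.2%.

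With all 400 women it is 86.9%. The stated figure of more than 85% reproduces. At a 30% reduction (p1 = 0.315) the same formula gives 78.7% with 392 women. These values are for the test without continuity correction; with one, power at 392 is 83.7%. The plan does not say which is meant.

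**2. Is gestational age prognostic?** Summing the 5.1 table rows, and reading the 32-34 week row as 32 to <34:

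- <32 weeks: (10 + 11 + 18)/(13 + 15 + 26) = 39/54 = 72%
- 32 to <34 weeks: 19/39 = 49%
- ≥34 weeks: (20 + 12 + 22 + 3 + 2 + 1)/(56 + 35 + 57 + 17 + 8 + 2) = 60/175 = 34%

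Chi-square is 24.5 on 2 df. The rows total 118/268, so 295 − 268 = 27 women and 141 − 118 = 23 cesareans are not placed in the table.

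**3. Power with and without stratification.** Simulation with 200,000 trials per scenario: 392 women, simple 1:1 randomization, the three-group mix above, group rates scaled to 45% overall (73.8%, 49.8%, 35.0%), and the same relative reduction in each group (an assumption). The pooled chi-square is compared with a three-stratum Mantel-Haenszel test, neither with continuity correction. The Monte Carlo standard error at 86% is √(0.86 × 0.14/200,000), about 0.08 points. Gains are taken before rounding.

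| Scenario | 33%: unadjusted / stratified | Gain | 30%: unadjusted / stratified | Gain |
|---|---|---|---|---|
| Table mix and gradient | 86.0 / 88.2 | 2.2 | 78.7 / 81.4 | 2.7 |
| 27 unplaced women all <32 weeks | 86.2 / 89.0 | 2.8 | 78.8 / 82.3 | 3.5 |
| 27 unplaced women all ≥34 weeks | 86.0 / 87.1 | 1.1 | 78.7 / 80.1 | 1.3 |
| Half the gradient | 86.0 / 86.3 | 0.3 | 78.7 / 79.1 | 0.4 |
| Half the gradient and unplaced ≥34 weeks | 86.2 / 86.2 | ≤0.1 | 78.9 / 79.0 | 0.1 |
| No gradient | 86.2 / 86.0 | −0.2 | 78.8 / 78.6 | −0.2 |
| One cut at 34 weeks | 86.2 / 88.0 | 1.8 | 78.8 / 81.0 | 2.2 |

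Cross-check: the share of outcome variance explained by gestational age in the table is R² = 0.072 (ten rows, adjusted for degrees of freedom) to 0.085 (linear). Replacing n by n/(1 − R²) in the step 1 formula gives 88.6% to 89.0% at 392, slightly above the simulation.

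In the step 1 formula, 419 women give 88.3% and 81.3% at the two effect sizes. The table-mix gain is therefore worth about 419 − 392 = 27 women, or 27/132 ≈ 0.2 years at the recruitment rate in 5.4.

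**4. Adjusting only after imbalance.** The share of the 2.2 points that is kept depends on the trigger:

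- Three-group chi-square on gestational age: 86.2%, keeping about 0.2.
- t test on gestational age: about 0.3.
- Any of the five listed variables significant at 5% (assuming the other four are independent and not prognostic): adjustment occurs in 1 − 0.95⁵ ≈ 23% of trials, keeping about 0.5 to 0.6.

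**5. Type I error at a single final analysis.** Unadjusted 5.0%; stratified 5.0%; adjust-if-imbalanced (first trigger) 4.8%; either result claimable, about 6.5%. At a 33% reduction the two tests disagree at 0.05 in 4.9% of trials: 3.6% significant only when stratified, 1.3% only when unadjusted.

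**The case against.** The strongest reply is that nothing is broken. The unadjusted test delivers the promised power, and naming the plain chi-square as primary would close the gap just as well. That stands as far as the ambiguity goes; stratification is the better choice only because it also gains power at almost no risk.

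The gain is also conditional, and this stands in full. The table leaves out 27 women. The cohort is not described as limited to an unfavorable Bishop score or to "Cervical dilation 2cm or less". It pools gestational hypertension with preeclampsia, whereas sections 3.4.1 and 3.5.2 to 3.5.4 name preeclampsia only and the title, aims and 3.3 name both. The gradient lies mostly below 34 weeks: using the R² within women at 32 weeks or more, the gain is about 0.4 points. The proposed cuts were chosen from the same table that supplies the gain, although a single cut still gives 1.8 points.

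A reader might infer that adjust-if-imbalanced inflates type I error. It does not: the simulated rate is 4.8%. The figure of about 6.5% requires whichever result is significant to be claimable, and no section permits that.

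Finally, 5% holds for one final analysis. Section 5.2 plans looks at least yearly, timed at the PI's discretion. If each of three looks could be claimed at 0.05, the stratified test would reject in about 11% of null trials. That is an assumption, since 5.2 says stopping would not rest on statistics alone. It is a separate matter that this change does not address.

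**Conclusion.** The point holds as an unspecified primary analysis with an inexpensive improvement available. Prespecified adjustment for gestational age adds about 2 points of power at a 33% reduction (86% to 88%) and a little over 2.5 at 30% (79% to 81%), if the trial enrols the table's mix and gradient and the relative effect is similar across gestational ages. Allowing for the limits of the table, the gain is roughly 0 to 3 points at 33%, and up to 3.5 at 30% in the most favorable case. If adjustment is triggered only by imbalance, about 0.2 to 0.6 of the 2.2 points is kept.

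A reader might conclude that the trial is underpowered or that 2 points are assured. The documents support neither: the stated power reproduces, and the gain rests on an incomplete table from a cohort that may differ from the women enrolled. The need to name one deciding analysis does not depend on the size of the gain.

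**What to change.** In 5.5, name one primary analysis of cesarean delivery: a Mantel-Haenszel test stratified by gestational age at randomization (<32, 32 to <34, ≥34 weeks), two-sided 5%, without continuity correction. Report the Mantel-Haenszel risk ratio with its 95% CI, which matches the relative reduction in 5.1, together with the risk difference. State that it applies whatever the baseline comparisons show, and make the unadjusted chi-square a sensitivity analysis. Say that the 5% refers to the single final analysis, with the interim looks in 5.2 handled separately.

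The cost is two or three sentences, with no new data, no extra women and no change to randomization. If gestational age proves unrelated to cesarean delivery, about 0.2 points of power are lost.

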6.0 Medication

6.1 Study drug: Isosorbide mononitrate is a drug used principally in the treatment of angina pectoris and acts by dilating the blood vessels so as to reduce the blood pressure. Research on extended release Isosorbide mononitrate as a cervical ripener to reduce time at hospital to birth is supportive. Isosorbide mononitrate is an active metabolite of isosorbide dinitrate and exerts qualitatively similar effects. It reduces the workload of the heart by producing venous and arterial dilation. By reducing the end diastolic pressure and volume, isosorbide mononitrate lowers intramural pressure, hence leading to an improvement in the subendocardial blood flow. The net effect when administering isosorbide mononitrate is therefore a reduced workload for the heart and an improvement in the oxygen supply/demand balance of the myocardium.

For purpose of this study 30mg Isosorbide mononitrate suppositories and matching placebo have been compounded by an investigational pharmacy using using a commercial extended release tablets formulated into suppositories by SBH Medical and IDS an investigational pharmacy will manage the storage and dispensing. A prototype suppository was used to determine feasibility. Potency testing was performed to get initial baseline then rechecked in 90 days, the results supported the shelf life and proof of concept (potency) on the suppositories. Per State Board of Pharmacy, Investigational Drug Service are not allowed to possess more than 7 days worth of non-patient specific compounded medication, and given our expected enrollment of approximately 5-6 patients per week, they will store 20 tablets of compounded medication/placebo. Suppositories will be refrigerated, and BUD is 30 days, protected from light and moisture.

The suppositories are manufacturer by:
SBH Medical, Ltd
[name] R.Ph. ([contact])
[name]
[contact]; [contact]
Web:

And will be stored at:
Investigational Drug Service
[name]
[name]
[name]

6.1 Reported adverse reactions:

Headache
Tiredness
Sleep disturbances
Gastrointestinal disturbances
Hypotension
Poor appetite
Nausea

Other reactions that have been reported less frequently with isosorbide mononitrate modified release tablets include tachycardia, vomiting, diarrhea, vertigo and heartburn

